1. INTRODUCTION

1.1 ABSTRACT

This study seeks to improve clinical care for peripheral and central vestibular disorders by translating recent advances in vestibular physiology to clinical practice. Vertigo and dizziness lead to ~4.4 million US emergency department (ED) visits annually at a cost of roughly \$10 billion. Most of the estimated 1 million patients with peripheral (inner ear) vestibular causes for their symptoms are over-tested, misdiagnosed, and undertreated. Each year in the United States (US), hundreds of millions of dollars are spent on neuroimaging (~\$500M CT, ~\$100M MRI) trying to detect the 3-5% of patients who have life-threatening posterior fossa strokes causing their vertigo—yet one-third of these vestibular strokes are missed. Accurate, early, and efficient diagnosis will save lives and reduce costs through prompt and appropriate treatments applied in the ED in real time.

Our team has studied dizziness in the ED for more than a decade. We have developed a new approach to differentiate benign peripheral causes from dangerous central ones by careful assessment of three vestibular eye movements (**HINTS**: Head Impulse, Nystagmus, Test of Skew) and hearing. Our approach enables rapid physiologic diagnosis at the bedside with greater accuracy than MRI brain scans in the first two days after the onset of acute, continuous vertigo or dizziness. This approach has been validated in over 200 patients. Similar, well-established bedside techniques (e.g., Dix-Hallpike test) work to diagnose intermittent, position-provoked vertigo. Unfortunately, these eye movement tests are unfamiliar to most ED providers and even to many specialists. A video-oculography (VOG) device that measures these eye movements quantitatively has the potential to transform diagnosis of acute dizziness and vertigo. The device is easy to use, measures eye movements accurately, and requires no more patient cooperation than a routine bedside exam of the cranial nerves by a specialist. We have shown initial proof that the device correctly diagnoses acute vestibular strokes.

The **AVERT** Trial (**A**cute **V**ideo-**O**culography for **V**ertigo in **E**mergency **R**ooms for **R**apid **T**riage) is a multicenter, randomized, Phase II clinical trial of VOG-guided vs. standard care to improve diagnosis and initial management for patients with a chief symptom of vertigo or dizziness suspected to be of vestibular cause. We will recruit 226 adults from four EDs. We will perform bedside VOG and hearing testing on all subjects, who will then be randomized to VOG-guided vs. standard care. In the VOG arm, patients will be diagnosed and treated according to a standard, predefined protocol guided by VOG results using automated, evidence-based decision rules. We will compare the impact of this VOG-guided care pathway relative to standard care on ED diagnoses, diagnostic resource utilization, costs of diagnosis, treatments applied, and short-term outcomes. A logistical pilot study will be conducted to refine study test procedures and data collection tools prior to initiation of the main trial.

We hypothesize that VOG-guided rapid triage (VRT) will accurately, safely, and efficiently differentiate peripheral from central vestibular disorders in ED patients presenting acute vertigo or dizziness, and that doing so has the potential to improve post-treatment clinical outcomes for these patients.

1.2 OBJECTIVES

- 1.2.1 To measure the impact of VRT on diagnosis and initial management in ED vertigo/dizziness.
- 1.2.2 To measure the impact of VRT on initial diagnostic work-up costs in ED vertigo/dizziness.
- 1.2.3 To compare short-term clinical outcomes in those correctly diagnosed vs. those misdiagnosed.
- 1.2.4 To develop a training library of educational materials related to eye-movement interpretation.
- 1.2.5 To measure the diagnostic accuracy of expert interpretation of VOG in ED vertigo/dizziness.

2. BACKGROUND

Rapidly differentiating acute central from peripheral vestibular disorders is a major public health problem relevant to NIDCD¹ and NIH.² There are ~4.4 million US emergency department (ED) visits for vertigo or

dizziness at a cost of ~\$10 billion/yr.³ The ~1 million with peripheral vestibular causes are over-tested,⁴ misdiagnosed,⁵ and undertreated.⁶ Hundreds of millions of dollars are spent on brain imaging trying to rule out dangerous central vestibular causes such as stroke,³ yet one third of vestibular strokes are missed initially.⁷

ED physicians rank vertigo as a top priority for developing better diagnostic tools.⁸ Misconceptions^{9,10} drive ED clinical practice, resulting in both overuse and underuse of diagnostic tests.⁴ Patients with inner ear conditions such as vestibular neuritis (or labyrinthitis) and benign paroxysmal positional vertigo (BPPV) are often imaged and admitted unnecessarily⁴ instead of being treated and discharged. Patients with dangerous brainstem or cerebellar strokes may be sent home without critical stroke treatments, sometimes resulting in serious harm.¹¹

Over the past decade our team has documented the problem and built solutions to help close this quality of care gap.^{2-7,9,10,12-43} Multiple research studies, systematic reviews, and guidelines confirm that correct diagnosis for vestibular neuritis,⁴⁴⁻⁴⁶ BPPV,⁴⁷⁻⁵¹ and vestibular stroke,^{4,21,29,38} should be based on vestibular eye exams. We have developed a clinical decision rule based on such eye exams that distinguishes central from peripheral causes in acute vertigo more accurately than early MRI.^{4,21,38} Unfortunately, eye findings (e.g., head impulse, nystagmus type) require visual interpretation and can be subtle. Many clinicians are unfamiliar with their use.⁵

A device measuring these eye movements could transform diagnosis of vertigo in the ED. A portable video-oculography (VOG) device is approved by the FDA for vestibular testing. Its technical performance has been validated in the lab,^{52,53} and it is already routinely used in the assessment of peripheral vestibular patients in otolaryngology clinics.⁵⁴⁻⁵⁶ We recently showed that it can accurately diagnose strokes in the ED.³³ Integration of this device into daily ED practice could allow rapid and accurate diagnosis of vestibular neuritis, BPPV, and stroke—in total accounting for roughly one third of ED dizziness patients.^{57,58}

3. STUDY PROCEDURES

Randomized controlled trial (individual patient randomization), parallel design (1:1) (Figure 1). Patients screened but not eligible for randomization will be enrolled in an observational arm that undergoes limited follow-up to ascertain for clinical outcomes, particularly stroke events.

[figure not shown]

Figure 1. AVERT Trial patient flow. R = randomization. The VOG-guided rapid triage (VRT) algorithm selects a predetermined care pathway using decision rules. If the VRT algorithm diagnosis is peripheral, the patient will be slated for treat and discharge from the ED, followed by same-day safety MRI. ED providers may go ‘off protocol’ and insist on admission for safety, and may choose to consult another provider (e.g., ENT physician, vestibular physical therapist) for treatment of BPPV or vestibular neuritis if study treatment procedures appear ineffective. If the VOG diagnosis is equivocal, a neurology consultation is required, with subsequent management determined by ED provider and consultant(s) working together. The requirement for neurology consultation may be waived in cases where doing so could not feasibly be accomplished within a reasonable time frame; in such a case, the ED provider would determine subsequent management without the assistance of a neurologist. If the VOG diagnosis is central, the research team will request that the ED provider order a neurology consultation, neuroimaging (MRI), and admit the patient for further evaluation and testing, even if the ED provider believes the patient has a peripheral cause; a note to this effect will be placed in the patient’s medical chart as part of the research record. The ED provider will make the final decision whether to admit the patient. If the ED provider elects to discharge the patient, this would be documented as a protocol deviation. Funds permitting, we will also obtain 6-month phone follow-up.

The logistical pilot study is being conducted to refine study test procedures, data collection tools and examine VOG-guided rapid triage (VRT) reports prior to initiation of the main AVERT Trial. Study coordinators will verify that VOG quantitative outputs are complete and accurate before results are submitted to the clinical trials data warehouse. A designated centralized eye movement expert will review all VOG tests (videos, tracings, summary values and the automated algorithm classification) after VOG data collection and provide an eligibility determination and diagnostic classification, independent of the automated VRT algorithm result. The expert human interpretation will either agree or disagree with the eligibility and classification determined by the automated algorithm. If disagreement occurs, the human expert classification will determine eligibility (for all) and VRT pathway of care (for those randomized to the VRT arm of the study). These findings will be compared to the automated results output from the VOG device for quality assurance and to evaluate testing accuracy and sensitivity of the VOG-guided results. This process will continue in the main trial, if necessary, until confirmation of VOG testing result accuracy is established and verified. Subjects enrolled in the logistical pilot study may undergo some, but not all, study procedures scheduled for the main trial.

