Trial Arm 1 VRT (intervention arm): VOG-based logic rules determine rapid triage pathway

- report includes direct device output (physiologic traces, quantitative measures) plus most likely diagnosis, category, and clinical trial care pathway (peripheral, equivocal, central) instructions
- the VOG results become part of the patient's clinical record

The roles of the ED provider in the care of patients in the VOG arm will be as follows:

- assess illness severity and appropriateness of the patient for VOG testing and the study protocol
- exclude obvious general medical conditions
- take over diagnostic decision-making for patients in whom VOG is equivocal (with consultant input, if available)
- intervene to deviate from VRT pathway if they are concerned about safety for patients in the VOG arm

Note: these are the same roles anticipated for ED providers if the VOG device were used for clinical practice

Trial Arm 2 Standard Care (control arm): usual ED care plus VOG exam, no VOG report generated

- no VOG automated interpretation or summary report will be generated; the computer-based randomization algorithm does not generate a VOG report or pathway using logic rules in the control (standard care) arm

The roles of the ED provider in the care of patients in the standard care arm will be as follows:

- assess illness severity and appropriateness of the patient for VOG testing and the study protocol
- exclude obvious general medical conditions
- all diagnosis, consultation, treatment, and disposition decisions will be made by the treating ED provider(s)

5.1.3 Expert Human VRT Double-Check: The VRT algorithm outputs in the intervention arm will be double-checked by expert neuro-otology fellows or faculty in real time to ensure accuracy; human judgment will “trump” VRT if there is disagreement (or if, for technical reasons, the real-time algorithm is not able to be generated – for example, as with internet connectivity problems or during development). The expert human double-check procedure will be in place at the start of the main trial, and we anticipate it will remain in place until the VRT algorithm is refined (as per pre-specified adaptations during the trial period) such that it appears accurate and safe.

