Algorithm Refinement: It is pre-specified that the VRT algorithm will be adapted iteratively during the trial. The algorithm performance in the VRT arm of the live trial will be monitored from the outset through the use of a human double-check procedure (described above in Section 5.1.3). The human double-check will remain in place until the algorithm performance is sufficient to be considered safe for unattended use, in consultation with the DSMB. The algorithm will be refined as frequently as necessary as long as the human double-check remains in place, and afterwards (if the human double check is removed before trial end) based on a schedule determined by the lead study biostatisticians. In the interest of being able to conduct an end-of-trial analysis using the ‘optimized’ algorithm, modifications to the algorithm during the trial will be restricted to results from the VRT or observational arms of the trial; in this way, the optimized algorithm can be run on the SOC arm results without concerns for overfitting the algorithm to the data (i.e., a ‘split-half’ analysis).

Outcome assessment: The ED diagnosis will have been elicited from ED providers by study personnel as a forced choice diagnosis. For the primary outcome, a correct “ED Provider Diagnosis” requires that the “Adjudicated Final Diagnosis” is the same diagnostic category. The VRT diagnosis will be assigned automatically by the online algorithm in real-time. However, as long as the algorithm is being iteratively refined

during this Phase II trial, the human expert double-check procedure will remain in place. In this context, the primary trial outcome will be based on the actual VRT-based care delivered to the patient (regardless of whether that result was generated by the algorithm or modified by the expert human review). This approach is necessary to maintain alignment with the structure of the study as a randomized trial. Additional analyses will test the diagnostic accuracy of both the algorithm as rendered and the end-of-trial ‘optimized’ algorithm.

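### Section 3 shows the expert the algorithm's answer yet calls the expert's reading independent of it, so the agreement used for quality assurance is a prompted figure

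*Protocol*

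**What the plan says.** **Protocol section 3** describes a designated central expert who "will review all VOG tests (videos, tracings, summary values and the automated algorithm classification) after VOG data collection and provide an eligibility determination" and a "diagnostic classification, independent of the automated VRT algorithm result". The result is framed as a verdict on the algorithm: "The expert human interpretation will either agree or disagree with the eligibility and classification determined by the automated algorithm". The expert's findings are then "compared to the automated results output from the VOG device for quality assurance and to evaluate testing accuracy and sensitivity of the VOG-guided results". The process starts in the logistical pilot and runs on into the main trial, if necessary, "until confirmation of VOG testing result accuracy is established and verified".

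**Protocol section 5.1.3** sets up the main-trial version: "The VRT algorithm outputs in the intervention arm will be double-checked by expert neuro-otology fellows or faculty in real time to ensure accuracy". It lists what the reviewer looks at (room and eye video, eye and head traces, key history). The algorithm's classification is not on that list, and nothing says it is withheld. This review is limited to the VRT arm.

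**Protocol section 9.1 (Algorithm Refinement)** gives the double-check a monitoring role: "The algorithm performance in the VRT arm of the live trial will be monitored from the outset through the use of a human double-check procedure". The check stays until performance is judged good enough for unattended use, in consultation with the DSMB. Neither the protocol nor the SAP states an agreement rate, a kappa or a numerical criterion for removing it.

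**The concern.** A reading made with the algorithm's answer on view is not independent of that answer. The documents require no reading to be recorded before the output is seen. Followed as written, section 3 therefore yields a prompted agreement figure under the label of an independent one.

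Three uses of the reading are exposed:

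- **Quality assurance.** The expert-algorithm comparison in section 3 is the stated check on the accuracy and sensitivity of the VOG-guided results.
- **Monitoring and removal of the double-check.** The DSMB may be shown agreement and override rates when removal is discussed. With no numerical criterion, much depends on what those rates mean.
- **Error capture.** The double-check exists to stop wrong algorithm calls reaching the patient. A reviewer who sometimes goes along with the display stops fewer of them.

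**Working it through.** **Step 1. The passages side by side.**

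| Question | Section 3 | Section 5.1.3 |
|---|---|---|
| Is the algorithm classification among the materials? | Yes, by name | Not listed |
| Is the reviewer masked to it? | No | Not stated |
| Is a reading locked before the output is shown? | Not described | Not described |
| Is the reading called independent? | Yes | No such claim |
| Which patients? | All VOG tests; eligibility for all | VRT arm only, after randomization |

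The contradiction is plain in section 3. In 5.1.3 the point is silence. The algorithm diagnosis is already determined when the reviewer is called, and the reviewer is described as changing its category, so the output is likely to be visible; the text does not settle it. The two scopes also differ. The description of the standard care arm in section 5.1 adds that no automated interpretation is generated there.

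**Step 2. Direction and possible size.** The plan has no figure to reproduce here, so this is an illustration. Inputs:

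- *p*, algorithm accuracy: assumed, 0.90 and 0.75.
- *e*, unaided expert accuracy: 187/190 = 0.984, from protocol section 9.3. That figure is for separating peripheral from central causes in acute continuous vertigo; using it for the six-category reading is an assumption.
- *d*, the share of would-be disagreements in which the expert defers to the display: not in the documents, so 0 to 0.50 is shown.
- Expert and algorithm errors are assumed independent, and both-wrong is counted as disagreement.

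Formulas:

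- Agreement = *pe* + *d*(1 − *pe*)
- Override rate = 1 − agreement
- Share of algorithm errors corrected = *e*(1 − *d*)

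With *p* = 0.90, *pe* = 0.90 × 0.984 = 0.886. With *p* = 0.75, *pe* = 0.738. At *d* = 0.25 and *p* = 0.90, agreement = 0.886 + 0.25 × 0.114 = 0.914.

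| *d* | Agreement, *p* = 0.90 | Override rate, *p* = 0.90 | Agreement, *p* = 0.75 | Algorithm errors corrected |
|---|---|---|---|---|
| 0 | 88.6% | 11.4% | 73.8% | 98.4% |
| 0.10 | 89.7% | 10.3% | 76.4% | 88.6% |
| 0.25 | 91.4% | 8.6% | 80.4% | 73.8% |
| 0.50 | 94.3% | 5.7% | 86.9% | 49.2% |

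Any *d* above zero pushes agreement up and error capture down. The distortion in agreement is larger for the poorer algorithm: at *d* = 0.25 it gains 6.6 points (80.4 − 73.8) when *p* = 0.75, against 2.8 points (91.4 − 88.6) when *p* = 0.90.

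**Step 3. Where the prompted reading does not enter.** Algorithm-only accuracy scores the real-time output, without the human check, against the Adjudicated Final Diagnosis (protocol 9.2.1, secondary outcome 5; SAP exploratory outcome 3). The optimized algorithm is tested in the standard care arm (secondary outcome 6; SAP exploratory outcome 4), where 5.1.3 excludes the double-check. The adjudication panel is masked to allocation, and its VOG input comes from two experts given only demographics, a structured history and bedside hearing results (protocol 9.1; SAP 2.1).

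**The case against.** The other side has a good case on consequences.

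- **An unprompted reading already exists.** The two masked experts in section 9.1 produce an Index VOG Diagnosis from materials that do not include the algorithm output, and section 6.3.9 names expert-algorithm concordance as a research question. So an unprompted concordance could be computed. This stands, but the documents do not tie that reading to the section 3 verification or to removal of the double-check.
- **Independent may only mean not bound by the algorithm**, since human judgment prevails under 5.1.3. That is possible, but section 3 uses the comparison to evaluate accuracy, where independence in the statistical sense is what counts.
- **Removal does not rest on agreement alone.** Correct. Section 9.1 brings in the DSMB and names no agreement criterion, and section 4.3.7 links algorithm refinement to patients whose final adjudication is complete.
- **Missed strokes have other backstops:** an index MRI for all VRT patients, the ED provider's freedom to leave the pathway, and the 1-week MRI. These limit harm. They do not make the double-check redundant: section 6.3.18 puts MRI sensitivity at about 80% in the first 24 hours.

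A reader might also infer that the primary comparison is biased toward VRT. The documents do not support this. Section 9.1 deliberately scores the VRT-based care actually delivered, whether set by the algorithm or changed by the expert. Wrongly retained algorithm errors are then part of the intervention's real performance and count against VRT. Nor does the text support saying that 5.1.3 shows the reviewer the classification; it leaves this open.

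**Conclusion.** The point holds in limited form. Section 3 contradicts itself on independence, and sections 5.1.3 and 9.1 do not say whether the main-trial reviewer is masked to the output they are checking. What is affected is the quality-assurance agreement, the override rate, the monitoring information that informs removal of the double-check, and the protection the check gives. The reference standard, the formal algorithm accuracy analyses and the validity of the primary comparison are not affected.

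The direction needs only that reviewers sometimes defer to a displayed answer. The size cannot be derived: the deference rate and algorithm accuracy are assumed, and the expert accuracy is borrowed from a narrower task. The tabulated figures show how the bias behaves and do not estimate it. The correction is worth making because it is cheap and the figure it protects may inform a safety decision.

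**What to change.** 1. In section 3, take the algorithm classification out of the first-pass materials.
2. In section 5.1.3, add: *The expert reviews the recordings, traces and key history, and records and locks an eligibility and diagnostic call in the EDC before the algorithm output is revealed. The expert may then confirm or revise that call. The post-reveal call drives care and the primary outcome, as now.*
3. Compute agreement and override rate from the locked first read. Also record how many initial disagreements are dropped after the reveal; that measures the deference rate, which is otherwise unknown.
4. Reconcile section 3 (all VOG tests, eligibility for all) with section 5.1.3 (VRT arm only), and state which patients have an algorithm output to compare.

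If locking is not adopted, delete the claim of independence and report the agreement as prompted.

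The cost is a change in EDC screen order, seconds of reviewer time on a review of about 10 to 15 minutes, and possibly a slightly lower reported agreement. No extra reader is needed. Section 5.1.3 already relies on the expert's judgment alone when the algorithm result cannot be generated, so an unprompted reading fits the existing workflow.

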4. ENROLLMENT CRITERIA & PROCESS

Performance sites are Johns Hopkins University (Bayview Medical Center [ED], Johns Hopkins Hospital [ED, clinic]), University of Michigan Hospital [ED, clinic], University of Illinois (OSF St. Francis Medical Center [ED, clinic]), The Mount Sinai Hospital [ED, Clinic], The Massachusetts General Hospital [ED], Massachusetts Eye and Ear [Clinic].

4.A. MRI standardization subjects

Healthy volunteers, up to 4, were recruited for the purposes of standardizing MRI machine settings and image acquisition protocols across sites. Some of the volunteers were staff traveling from the Coordinating Center (CC) to the performance sites in order to have the same person(s) undergo MRI scanning at each site to enhance MRI standardization across sites. Adults 18 years or older who were able to undergo MRI were recruited and granted their consent either under this protocol or in association with other locally IRB-approved protocols, depending on the study center. Prospective volunteers with a health condition that made it unsafe for the participant to have an MRI, including people with certain metal or foreign objects in their bodies, and pregnant women were excluded. Non-study staff volunteers were recruited in accordance with local IRB policies.

4.B. Dizziness subjects (ED patients at one of 5 academic-affiliated hospitals; consecutive sample during shifts)

For the main clinical trial, we expect to enroll (randomize) approximately 226 participants recruited from the ED across the five sites, approximately 75 per site (the Johns Hopkins and University of Michigan will each recruit a total of 75 subjects from all of their institutional ED sites combined). Recruitment will be consecutive during shifts (generally scheduled during the time window 8AM to 7PM weekdays). For the logistical pilot study, participants from the ED were screened and granted consent for participation across the three sites in a convenience sample to maximize effectiveness of trial procedure development.

